Secondary end-point analysis: Patient Reported Outcome (PRO) metrics. In this sub-aim, we hypothesize that therapeutic interventions will improve clinical symptoms as measured by PRO metrics. This is an important issue to resolve as only a few prior studies have shown the clinical efficacy of therapeutic interventions. In fact, several studies have shown dissociation between histology (eosinophil levels) and clinical improvement^{31,32}, but these studies have not used validated metrics for measuring symptoms. The measurement of pre/post diet symptoms using tools that have undergone at least some validation is a novel aspect of our study. While we have made substantial progress with the development and validation of a number of PRO measurements, there is still not agreement around the best measurements, related in part by the uncertainty of whether these instruments truly measure meaningful and accurate parameters. Agreement about these measurements has significant bearing on the eventual FDA approval of therapeutic agents³³. As such, we will take several approaches in this sub-aim. First, we will employ EoE specific measurement tools, including the adult EoE dysphagia questionnaire, EoE Adult Symptom Score Activity Index (EESAI), and the adult EoE quality of life score (EoE-QOL-A^{36,37,38,39}). In addition, we will also employ generic Health Related QOL metrics, such as PROMIS General Health Questionnaire, and eventually compare the changes in disease specific versus general health questionnaires. These PROs will be assessed at the screening visit and again at the end of each treatment phase to assess the effects of treatment.

AIM 2: To determine clinical parameters and biomarkers that predict responsiveness to therapies.

2a. Clinical phenotypes. In this sub-aim, we hypothesize that certain patient phenotypes will correlate with response to each intervention in the trial. We will assess the relationship between response to 1FED, 6FED, and SGC on age, height, weight, BMI Z-score, race, ethnicity, allergic status, participant compliance (defined by diet and SGC usage diaries), and screening eosinophil levels as readouts.

2b. Skin testing. In this sub-aim, we hypothesize that skin test results (prick testing to the 6 foods in the 6FED and atopy patch testing to milk) will provide significant predictive value for outcomes in the diet trial phases. While a substantial body of work has already been done concerning skin testing, there still remains

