- 2d. Assessment of milk-driven T cells.** In this sub-aim, we will perform exploratory studies designed to test the presence and significance of circulating milk-specific T cells in EoE patients. We will test the hypothesis that milk-specific T cells will be primarily CD4+, IL-5+, IL-13+, consistent with prior work.⁴⁷⁻⁴⁹ Furthermore, we will test the sub-hypothesis that the level of milk-specific T cells will positively correlate with positive atopy patch tests to milk and the response rate to milk elimination (1FED and secondarily 6FED, which also contains milk). The frequency of Th2 cells will be determined by FACS analysis, and milk-specificity will be estimated by milk protein stimulation in vitro, particularly looking at CD154 induction, a marker of T cell activation. These exploratory studies, will be performed with shipped blood samples, by [name], as published.^{47,48,50,51} The study will be limited to a pilot analysis of patients who only enter the 1FED and we will compare patients with positive and negative skin tests (prick and patch).
- 2e. Predictive Biomarker-analysis of EoE transcriptome.** In this sub-aim, we aim to identify biomarkers that may predict responsiveness to any or all of the treatment interventions associated with this trial. Determining such a biomarker would have a profound effect on disease management as patients could be quickly triaged into different therapies, e.g. diet versus SGC; thus saving time, reducing the number of endoscopies and potentially improving quality of life issues. As such, in this sub-aim, we will perform the EDP analysis on baseline biopsies, focused on identifying transcript levels that differentiate patients that respond to each of the interventions. In preliminary studies, we have conducted this type of analysis on patients that recently participated in the randomized controlled trial of high dose fluticasone (1760 mcg per day) for the treatment of EoE. Forty-two participants were enrolled in this study (28 FP, 14 placebo). After 3 months, 65% of FP-treated and 0% of placebo-treated participants had complete remission ($P = 0.0001$); 12% of FP-treated and 8% of placebo-treated participants had partial remission. Of the FP-treated participants in complete remission, 73% continued in complete remission, and 20% were in partial remission after halving the daily FP dosage.⁵³

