13.4.5 Analyses of Exploratory Endpoint(s)/Outcome(s)

Exploratory objectives are detailed below:

1. To evaluate the clinical and psychosocial effect of each therapy utilizing surveys to assess EoE symptoms and problems/feelings related to eating.
2. To determine if any clinical parameters predict response to therapeutic intervention.
3. To determine if any biomarkers including serum food specific IgE, CRD, and IgG4 predict response to therapeutic intervention.
4. To determine if skin testing, in the form of prick and patch testing, predicts response to therapeutic intervention.
5. To determine if milk-driven T cells in the blood positively correlate with milk atopy patch test results and effectiveness of dietary therapies.

At the start of the trial intake of the allergens will be determined and descriptive statistics will be used to describe how often/how much of the allergens were consumed as part of the usual diet. During the trial any accidental exposure will be documented and we can use descriptive statistics to describe how often/how much of the allergens were consumed accidentally.

To compare treatment groups at the end of Phase 1 for EoE symptoms and problems/ feelings related to eating, the generalized linear mixed effects model described for the secondary endpoints will be used with the link function appropriate for the endpoint. Imputation for missing data will follow that described for the secondary endpoints.

To evaluate the ability of biomarkers to predict response to therapeutic intervention, multivariable logistic regression analysis will be conducted with remission/no remission as the dependent variable and biomarker levels as the independent variables. Multi-collinearity of the independent variables will be assessed. The area under the receiver operating characteristic curve (AUROC) will be estimated along with 95% confidence interval. This analysis will be conducted based on the remission status at the end of Phase 1. This analytic approach will be used to determine if skin testing predicts response to therapeutic intervention and to determine if milk-driven T cells predict response to intervention and to determine if T cells correlate with milk atopy patch test results. All exploratory analyses will be conducted at the nominal two-sided $\alpha=0.05$.

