Analyses of Exploratory Endpoint(s)/Outcome(s)

Exploratory Variables:

- 1) Change in Patient Reported Outcome (PRO) metrics (pre- minus post- treatment)
 - a. EoE Adult Symptom Score Activity Index (EESAI)
 - i. VDQ, AMS, Overall PRO
 - b. Adult EoE Quality of Life Score
 - i. Social impact, emotional impact, disease anxiety, eating/diet impact, choking anxiety
 - c. PROMIS General Health Questionnaire
- 2) Clinical parameters
 - a. Baseline disease activity measures (peak eosinophil count, EREFS, HSS)
 - b. Body mass index (BMI)
 - c. Presence of atopy and specific atopic diseases (e.g., is asthma associated with tx response/non-response)
 - d. Demographics (sex, age, race)
- 3) Biomarkers
 - a. Serum food specific IgE

- b. CRD – food specific components for IgE and IgG4
 - c. Serum food specific IgG4
 - d. EDP score
- 4) Skin testing results
- a. Skin prick tests to milk, egg, wheat, soy, peanut, shellfish, fish, and 5 tree nuts.
 - b. Positive is defined as ≥ 3 mm.
- 5) Milk driven T-cells
- a. T-cell count
 - b. Cytokine levels

Exploratory objectives are detailed below:

- 1) To evaluate the clinical and psychosocial effect of each therapy utilizing patient reported outcomes (PROs) to assess EoE symptoms and problems/feelings related to eating.
- 2) To evaluate factors predicting treatment response including
 - a) Clinical parameters
 - b) Serum food specific IgE, CRD, and IgG4
 - c) Skin testing results, in the form of prick and patch testing
 - d) Milk-driven T cells in blood

To test hypotheses for exploratory objective one, we will compare the treatment arms using general linear mixed models as described for the secondary outcome measures. To test hypotheses for exploratory objective 2, we will compare responders to non-responders using the generalized linear mixed effects model using the link that is appropriate for the endpoint (i.e. logit for binary, cumulative logit for ordered multinomial categories, identity for continuous). Covariates will be considered as appropriate. For continuous data, appropriate transformations will be considered (e.g. log, square root, rank) to satisfy the assumptions of the analyses.

Adverse Events

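### The exploratory predictor analyses prespecify no diet term, marker-by-diet interaction or by-diet model, although the protocol's aims for them are diet-specific

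*SAP*

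**What the plan says.** The aims are specific to the treatment. In Protocol 4.4, sub-aim 2a reads "we hypothesize that certain patient phenotypes will correlate with response to each intervention in the trial", and sub-aim 2e is "focused on identifying transcript levels that differentiate patients that respond to each of the interventions". Section 3.1 states the phenotype hypothesis in the same way. The secondary endpoints in the synopsis link milk component testing and circulating milk-specific T cells to the 1FED response in particular.

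The methods are not specific to the treatment. For exploratory objective 2 the SAP says "we will compare responders to non-responders using the generalized linear mixed effects model" and adds "Covariates will be considered as appropriate". Protocol 13.4.5 plans a multivariable logistic regression "with remission/no remission as the dependent variable and biomarker levels as the independent variables", with an AUROC, and states: "This analysis will be conducted based on the remission status at the end of Phase 1". At that point about half the participants are on each diet. The nominal level is two-sided 0.05 ("All exploratory analyses will be conducted at the nominal two-sided").

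The SAP does bring in the arm elsewhere. For exploratory objective 1 (patient-reported outcomes), "we will compare the treatment arms using general linear mixed models". Phase 2 remission is also to be reported separately by Phase 1 diet. Protocol 4.4 (sub-aim 2d) and 10.2 confine the T-cell pilot to 1FED entrants; the SAP lists T-cell measures without that restriction.

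**The concern.** A marker may matter on one diet and not on the other. This is plausible for milk markers: 1FED removes milk only, while 6FED removes five other food groups as well. A single responder versus non-responder contrast, or a regression without diet, then gives an average of two different effects. A marker useful for choosing 1FED could be diluted until it is missed, and a marker with opposite effects on the two diets could disappear. The resulting AUROC would describe a mixed population rather than patients on either diet.

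The open covariate sentence does not settle the matter. It would allow a diet main effect, but a model with diet as a main effect still gives one common marker effect. It also leaves the decision about diet open until the data are in hand, across many markers tested at a nominal 0.05.

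**Working it through.** **The plan's own figure.** Protocol 13.6 gives 60 per group for 45% versus 70% remission, two-sided alpha 0.05 and at least 80% power. With pooled variance under the null, n = [1.96·√(2 × 0.575 × 0.425) + 0.8416·√(0.45 × 0.55 + 0.70 × 0.30)]² / 0.25² = (1.370 + 0.569)² / 0.0625 ≈ 60.2, so 61. Power at 60 is 0.799 by this approximation, and 0.796 (noncentral chi-square) or 0.806 (exact enumeration) for the likelihood ratio test that the plan names. The figure reproduces. The documents give no size or power for the predictor analyses.

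**Inputs.** From Protocol 13.6: remission 45% on 1FED and 70% on 6FED, 68 per arm. Assumed, because the documents give nothing: a binary marker with prevalence 30% or 50% in both arms, and the odds ratios (OR) below. Arm remission rates are held at 45% and 70% throughout.

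**Formulas.** The pooled remission rate at each marker level is the mean of the two arm rates. OR = [p₁/(1−p₁)] / [p₀/(1−p₀)]. SE² of a log OR = Σ 1/[n·p(1−p)] over the marker groups. Power ≈ Φ(|log OR|/SE − 1.96). For the interaction, the estimate is the difference of the two log ORs and its variance is the sum of theirs.

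**One case in full: prevalence 50%, OR 3 on 1FED, OR 1 on 6FED.**
- Marker-negative and marker-positive remission: 31.7% and 58.3% on 1FED; 70% and 70% on 6FED.
- Pooled: (31.7 + 70)/2 = 50.85% and (58.3 + 70)/2 = 64.15%. OR = (0.6415/0.3585)/(0.5085/0.4915) = 1.73.
- Pooled power (68 v 68): SE = √(0.0588 + 0.0640) = 0.350; 0.548/0.350 = 1.56; power 34%.
- Within 1FED (34 v 34): SE = √(0.136 + 0.121) = 0.507; 1.099/0.507 = 2.17; power 58%.
- Interaction: SE = √(0.257 + 0.280) = 0.733; 1.099/0.733 = 1.50; power 32%.

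**All scenarios, 68 per arm (prevalence 30% / 50%).**

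| OR on 1FED, 6FED | Pooled OR | Pooled power | Power within 1FED | Interaction power |
|---|---|---|---|---|
| 3, 1 | 1.76 / 1.73 | 30% / 34% | 52% / 58% | 28% / 32% |
| 3, 1/3 | 1.06 / 1.09 | 5% / 6% | 52% / 58% | 80% / 83% |
| 3, 3 | 2.79 / 2.77 | 70% / 81% | 52% / 58% | 5% (no interaction present) |

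**The same on the risk scale.** Suppose 50% prevalence, marker-positive versus marker-negative remission of 60% v 30% on 1FED, and 70% v 70% on 6FED. Pooled, this is 65% v 50%: a 30-point effect becomes 15 points. Normal-approximation power for the difference falls from 0.71 (34 v 34) to 0.42 (68 v 68), despite twice the patients. The interaction test (OR 3.5, log OR 1.25, SE 0.74) has about 40% power.

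**What the interaction can detect.** With no effect on 6FED and 68 per arm, 80% power needs a ratio of ORs of about 8.7 (prevalence 50%) to 11.9 (prevalence 30%).

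**The case against.** - **Pooling is not stated.** Neither document says that the diets will be combined, and the SAP's covariate sentence leaves room for a diet term. This stands. Pooling is the natural reading, because the SAP names the arm where it means to use it, but it is not a rule. A reader might infer that the trial is unable to show what predicts response to a given diet. The documents do not support that: the same data allow by-diet models, and the gap is in what is prespecified.
- **The milk markers are partly covered.** The protocol limits the T-cell pilot to 1FED and ties two endpoints to 1FED response. This stands for T cells. For milk components, the endpoint is diet-specific but the model in 13.4.5 is not.
- **Confounding.** At the planned rates, 6FED patients make up 0.70/1.15 = 61% of responders but 0.30/0.85 = 35% of non-responders. A reader might infer that marker and diet are confounded. They are not, for baseline markers: diet is randomised 1:1 within site (Protocol 13.3). A marker with no effect on either diet therefore has expected pooled remission of (45 + 70)/2 = 57.5% at both marker levels. The two percentages only restate the assumed diet effect. Randomisation gives no such protection to compliance (listed in sub-aim 2a) or to the week 6 blood draws, if those were used as predictors.
- **Pooling can be the better analysis.** With a common effect it costs little and has more power than one arm alone. This also stands, and it is why the interaction should be estimated rather than assumed either way.
- **The work is exploratory.** True, and the primary result does not depend on it. It is nevertheless the protocol's Aim 2.

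**Conclusion.** The point holds as a mismatch between aim and analysis. The aims are diet-specific; the stated predictor analyses contain nothing that makes the marker effect diet-specific, apart from the protocol's T-cell restriction. Run as written, they estimate one averaged effect per marker.

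The consequence depends on how the marker behaves: substantial dilution if it acts on one diet only, near-cancellation if the effects are opposite, and almost no loss if they are equal. The problem is effect heterogeneity, not bias from confounding. These sizes rest on assumed prevalences and odds ratios and on the planned 45% and 70% rates; they illustrate and do not predict.

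Two limits apply to any remedy. Phase 1 has no untreated arm, so a within-diet marker effect cannot separate general prognosis from response to that diet; only the interaction bears on the choice between diets. And a Phase 1 model says nothing about predictors of response to swallowed steroid, which sub-aim 2a also covers.

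**What to change.** In the SAP, for exploratory objective 2:

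1. Keep the protocol's logistic model with Phase 1 remission as the outcome, and add diet, marker × diet and site. This also settles the SAP's wording on link functions, which could be read as making a continuous marker the outcome.
2. Lead with the marker effect within each diet and its 95% interval.
3. Report the interaction estimate with its interval, labelled exploratory.
4. Carry the protocol's 1FED-only restriction for the T-cell analysis into the SAP.
5. State that the baseline measurement of each marker is the predictor.

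No new data are needed. The cost is two extra terms per marker (diet and the interaction), repeated over a long marker list, with wide within-diet intervals. Interaction power is about 30% to 40% in the one-diet-only cases worked above (OR 3 to 3.5), so a non-significant interaction must not be read as evidence that a marker works equally on both diets.

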Secondary Endpoint(s)	
 • Histology and endoscopy measures 
 a. Division of patients into complete (peak eosinophils ≤1/HPF) or partial (≤6 or ≤10) remission b. Histology Scoring system c. Endoscopic scoring system (EREFS) • Biomarkers pre- and post-treatment 
 a. Assessment of EDP Score • Patient Reported Outcome (PRO) metrics pre- and post-treatment 
 a. EoE Adult Symptom Score Activity Index, and Adult EoE Quality of Life Score b. PROMIS General Health Questionnaire • Clinical parameters and biomarkers to predict responsiveness to diet and SGC therapy 
 a. Correlation of clinical characteristics to response to therapy b. Assessment of predictive value of skin prick and patch allergy testing c. Correlation between presence of positive milk component allergy testing to response to 1FED d. Correlation of level of circulating milk-specific T cells with patch testing and response to 1FED e. Predictive biomarker-analysis of EoE transcriptome from EDP analysis on baseline biopsies in correlation to response to treatment.

Sample Size:	136
Study Duration	Minimum 18 weeks to maximum 27 weeks

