3. STUDY HYPOTHESES/OBJECTIVES

3.1 Hypotheses

We hypothesize that 6FED will be superior to 1FED, although we expect that a substantial (meaningful) percentage of patients will respond to 1FED.

We hypothesize that some patients who fail to respond to 1FED will respond to 6FED.

We hypothesize that some patients who fail to respond to 6FED will respond to SGC.

We hypothesize that HSS will more accurately quantify histological changes associated with EoE and be reversible following each therapeutic intervention. Furthermore, we hypothesize that some patients may show partial responses, where a subset of the HSS may be improved earlier or in dissociation with eosinophil levels, for example.

We hypothesize that molecular biomarkers will change (improve) with each treatment phase, at least in part. Furthermore, we hypothesize that biomarkers may reveal (a) novel insight into therapeutic resistance and/or relapse; (b) reveal patient sub-groups not identified by histology; and (c) ultimately prove to be readily usable biomarkers in clinical settings and possess personalized medicine value. If our hypotheses are proven to be correct, they have potential to transform monitoring of patients during therapeutic intervention, by identifying molecular markers that have therapeutic significance, and also by reducing the need for biopsies, particularly after therapy is initiated.

We hypothesize that the therapeutic interventions utilized in this study will improve clinical symptoms as measured by PRO metrics.

We hypothesize that certain patient phenotypes will correlate with response to each intervention in the trial.

We hypothesize that skin test results (prick testing to the 6 test foods and atopy patch testing to milk) will provide significant predictive value for outcomes in the diet trial phases.

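### For factors predicting treatment response, the SAP departs without explanation from the protocol's remission model and AUROC, so as written it tests association but does not report predictive value

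*SAP*

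**What the plan says.** **Protocol 13.4.5 (exploratory analyses).** For biomarkers, "multivariable logistic regression analysis will be conducted with remission/no remission as the dependent variable and biomarker levels as the independent variables". Collinearity is to be assessed, and "The area under the receiver operating characteristic curve (AUROC) will be estimated along with 95% confidence interval". Remission status is taken at the end of Phase 1. The method is then extended: "This analytic approach will be used to determine if skin testing predicts response to therapeutic intervention", and likewise for milk-driven T cells. On the error level: "All exploratory analyses will be conducted at the nominal two-sided" 0.05.

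**Protocol, targets.** The synopsis lists among the secondary endpoints "Assessment of predictive value of skin prick and patch allergy testing". Section 3.1 hypothesizes that skin test results "will provide significant predictive value for outcomes in the diet trial phases". Section 4.4 (2e) hopes that baseline transcripts will help to direct patients to one therapy or another.

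**SAP, Analyses of Exploratory Endpoint(s)/Outcome(s).** Objective 2 is still worded as prediction: "To evaluate factors predicting treatment response including" clinical parameters, serum markers, skin tests and T cells. The method is different: "we will compare responders to non-responders using the generalized linear mixed effects model using the link that is appropriate for the endpoint". The links offered are logit, cumulative logit and identity, with transformation of continuous data where model assumptions require it. The section names no dependent variable and contains no AUROC, sensitivity, specificity, joint marker model, collinearity check or significance level.

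**The concern.** The two documents give different analyses for one objective, and the SAP, the later and more detailed of the two on analysis, does not say why. If response is the grouping variable and the marker is what is modelled, the output is a difference in marker level with a p-value. That answers whether a marker is associated with response. It does not say how well the marker separates patients who will respond from those who will not, nor how the markers perform together.

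The protocol asks for the second kind of answer, at least for skin tests. The SAP lists many candidate markers (food-specific IgE and IgG4, components, EDP score, prick tests, T-cell counts and cytokines). Some may reach nominal significance while discriminating poorly, and a report that follows the SAP would not let the reader see this. With two analyses on file, the choice between them could also be made after the results are known.

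**Working it through.** **1. The texts side by side.**

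| Item | Protocol 13.4.5 | SAP, exploratory objective 2 |
|---|---|---|
| Dependent variable | Remission yes/no, end of Phase 1 | Not named |
| Role of markers | Joint predictors | Apparently the modelled endpoint |
| Collinearity check | Yes | Not mentioned |
| Discrimination | AUROC with 95% CI | Not mentioned |
| Site | Not stated for this model | Mixed model |

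The direction of the SAP model has to be inferred. Patients are grouped by response, and the link varies with the type of endpoint. An identity link and transformation of continuous data do not fit a categorical response, whether it has two levels or three, but they do fit a continuous marker.

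**2. Inputs for an illustration.** The documents give no figure for the marker analyses. Protocol 13.6 gives planning remission rates of 45% (1FED) and 70% (6FED) and 68 patients per arm. Those planning figures reproduce: the pooled normal formula gives 61 per group against the stated 60, and exact enumeration of the likelihood ratio test at 60 per group gives 80.6% power against the stated minimum of 80%. My own assumption is a marker that is normal with equal variance in responders and non-responders.

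- Responders: 68 × 0.45 + 68 × 0.70 = 30.6 + 47.6 = 78.2
- Non-responders: 136 − 78.2 = 57.8

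**3. What a just-significant marker is worth.** The smallest standardized difference with two-sided p = 0.05 is d = t(0.975, N − 2) × √(1/n₁ + 1/n₀). Under the normal model, AUROC = Φ(d/√2).

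| Set | n₁ / n₀ | d | AUROC |
|---|---|---|---|
| Pooled, N = 136 | 78.2 / 57.8 | 0.343 | 0.596 |
| 1FED, N = 68 | 30.6 / 37.4 | 0.487 | 0.635 |
| 6FED, N = 68 | 47.6 / 20.4 | 0.528 | 0.646 |

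With 1.96 in place of the t quantile, the AUROCs are 0.595, 0.632 and 0.643. With 120 evaluable patients (69 / 51), the pooled value is 0.601. The range is therefore about 0.60 pooled and 0.63 to 0.65 within one arm.

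**4. Does the direction of the model change this?** Hardly. For one binary marker without covariates, the odds ratio is the same in either direction. For a normal, equal-variance marker, a just-significant logistic regression would correspond to about the same AUROC. What is lost is the reported AUROC with its interval, and the joint model.

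**5. Precision if the AUROC is restored.** With the Hanley–McNeil standard error at an AUROC of 0.70, the 95% half-width is about 0.09 pooled (0.087) and about 0.13 within one arm (0.127 for 1FED, 0.128 for 6FED).

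**The case against.** Several objections stand and limit the point.

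- **The reversal is not stated.** A reader might infer that the SAP deliberately swaps outcome and predictor. It never names the dependent variable, and its list of links repeats the paragraph on secondary endpoints, so it may be carried-over text. Nor can one argue that remission is always binary here: the SAP defines complete, partial and no remission, and a three-level HSS remission, either of which a cumulative logit could model. The inference rests on the grouping by response, the identity link and the transformations.
- **The AUROC is not expressly withdrawn.** The SAP is silent on it, and it could be computed later from the same data.
- **The 0.60 does not measure harm from the SAP's direction.** A reader might take it that way, but step 4 shows that it applies equally to the protocol's model at its nominal 0.05. It shows only why discrimination has to be reported alongside significance.
- **Neither document says that a significant marker will be declared a predictor.** That weak markers would be presented so is a possibility, not a plan.
- **Some of the protocol asks only for association.** The synopsis speaks of correlating clinical characteristics, milk components and T cells with response, and 13.4.5 does not name clinical parameters when it sets out the AUROC approach.
- **Restoring the AUROC would not by itself serve the triage aim in 4.4 (2e).** Choosing between therapies needs evidence that a marker separates response to one from response to another, which a pooled AUROC cannot give.

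None of this removes the unexplained difference between the documents, or the absence from the SAP of any measure of predictive value.

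**Conclusion.** The point holds as an unexplained departure of the SAP from protocol 13.4.5. Followed as written, the SAP tests association for objective 2 and does not report the predictive value that the protocol's synopsis and section 3.1 name for skin tests, or the AUROC that 13.4.5 specifies for biomarkers, skin tests and T cells. That the marker becomes the outcome is the most natural reading, not a stated fact. If remission was meant as the outcome, the passage still needs correcting, because its links do not fit.

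The illustrative AUROCs rest on the planning rates, full recruitment and a normal, equal-variance marker. They support one conclusion: a p-value below 0.05 is compatible with weak discrimination, whichever variable is on the left of the model. The change is worth making because it is specific and cheap, but the analyses are exploratory and the primary result is unaffected.

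**What to change.** In the SAP's exploratory section, objective 2:

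1. Name remission at the end of Phase 1 as the binary dependent variable, with a logit link, site as a random effect (in keeping with the SAP's mixed models) and the markers as predictors.
2. Restore the multivariable model, the collinearity check and the AUROC with 95% confidence interval for biomarkers, skin tests and milk-driven T cells. Single-marker models alone would not restore what the protocol specifies.
3. Report the results by diet arm, and include diet in any pooled model. Restrict T cells to 1FED, since protocol 4.4 (2d) and 10.2 limit that pilot to 1FED patients.
4. Keep the comparison of marker values between responders and non-responders as a descriptive table.

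If the sponsor prefers the SAP's analysis, it should state and justify the departure from 13.4.5.

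The cost is a few sentences and a little more programming; no new data are needed. The downside is imprecision within an arm: half-widths of about 0.13 at an AUROC of 0.70, and only about 20 expected non-responders on 6FED at the planning rates.
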